2 OBJECTIVES

2.1 Pilot trial Primary Objectives

- 1. Specific Aim 1: Does nutritional supplementation facilitate cognitive function in adult breast cancer survivors, relative to persons who do not receive this supplementation?** We predict that adult breast cancer survivors receiving nutritional supplementation will experience improved cognitive performance as assessed by a battery of standardized tests of cognitive function. The current pilot study will evaluate the feasibility of administration of the nutritional supplement and placebo in this patient population and performing cognitive function testing at baseline and post supplementation.

2. **Specific Aim 2: Is the facilitation of cognitive function in the nutritional supplementation group mediated by changes in markers of oxidative stress and inflammation, relevant to cognitive performance?** We predict that persons receiving nutritional supplementation will exhibit larger changes in antioxidant markers and that these changes will serve to mediate or explain differences in the cognitive performance of the two groups. The current pilot study will evaluate the feasibility of administration of the nutritional supplement and placebo in this patient population and testing antioxidant levels at baseline and after the supplementation.

3. **Specific Aim 3: Does nutritional supplementation facilitate cognitive function in adult breast cancer survivors, relative to persons who do not receive this supplementation as indicated by changes in structural and resting-state functional markers observed utilizing the MRI/fMRI?** We predict that adult breast cancer survivors receiving nutritional supplementation will experience improved cognitive performance as assessed by a battery of structural and functional changes in imaging markers in the brain. The current pilot study will evaluate the feasibility of administration of the nutritional supplement and placebo in this patient population and performe structural and resting-state functional MRI to evaluate changes in these imaging markers at baseline and after the supplementation.

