3.0 SUMMARY OF STUDY PLAN

[figure not shown]
This pilot project is a randomized clinical trial of the feasibility of administering the nutritional supplement and placebo, performing a battery of cognitive function testing, structural and resting-state functional MRIs, and antioxidant levels at baseline and post supplementation in a target group of breast cancer survivors treated with chemotherapy. Prior to study initiation, the Human Subjects Committee will approve all study procedures. This goal of this pilot feasibility study is to provide a comprehensive assessment of a clinical trial's specific challenges as well as strategies to mitigate risks before a well- powered clinical trial can be proposed and implemented.

Research teams that use feasibility studies experience faster clinical trial accrual and significantly fewer delays in enrollment than those that forgo this preliminary assessment. A properly conducted clinical trial feasibility study can provide information regarding:

- Biomarker methodologies/estimations
- Effect size estimations
- Compatibility of the clinical trial treatments and assessments with current patterns of care
- Available patient population
- Likelihood of patients agreeing to participate in the clinical trial
- Potential modifications to clinical trial design and eligibility criteria to enhance enrollment
- Competing clinical trials
- Site capabilities
- Research infrastructure
- Personnel
- Equipment
- Regulatory requirements and timelines
- Local institutional review board/independent ethics committee (IRB/IEC) review timelines
- Investigator grant requirements and site contracts
- Projected patient enrollment rates.

The current feasibility pilot trial is to inform the research team of all these above challenges that occur with clinical trials and can contribute to the proposal and conduct of a well powered clinical trial.

Nutritional Supplementation (COGNUTRIN®) in Breast cancer Patients with Cognitive Impairment: Study Schema

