4.0 PARTICIPANT SELECTION

Women who have been diagnosed with stage I-III B breast cancer (BCa) and who have completed neoadjuvant or adjuvant treatment with anthracyclines and/or taxanes + or – Radiation therapy within the past 6 months (+/- 7 days) will be invited to be screened for eligibility to participate in this trial (subjects on concurrent endocrine therapy (TAM, Aromatase inhibitors are also eligible to participate as this is standard of care for this patient population). We will, in addition, expand our recruitment at the Moffitt Cancer Center to include the members of the Moffitt Cancer Center Affiliate Network (Total Cancer Care network consisting of 16 community hospital affiliates and 415 community oncologists statewide. With this additional network to recruit this patient population from, we are confident that we will be able to recruit the number of subjects needed for this study from each site. Based on the number of subjects that can be recruited from Moffitt, we conservatively estimate that we will recruit and retain 40 subjects during the 6 months recruitment period. Throughout the recruitment, data collection and retention period of this study we will focus on retaining high participation rates of an ethnically diverse population.

If women are already patients at Moffitt Cancer Center or one of its affiliates, they will be identified by one of the medical oncologists who are co-investigators in this trial based on the diagnosis and treatment received. Women who have been diagnosed with stage I-IIIB breast cancer (BCa) and who have completed neoadjuvant or adjuvant treatment with anthracyclines and/or taxanes + or – Radiation therapy within the past 6 months, (+/- 7 days) will be referred to the clinical research coordinator who will then invite these potentially eligible subjects to be screened for eligibility criteria to participate in this trial. All subjects referred to the research team from affiliate sites will be screened for eligibility. In this pilot clinical trial, all subjects, if identified as eligible based on initial screening in any other site other than the Moffitt Cancer center, will be required to come to the Moffitt cancer center if willing to continue to participate.

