Our criteria for inclusion of subjects in this trial is that subjects recruited are able to understand and sign the informed consent. The subjects must also be fluent English-speaking (Persons who are not fluent English speakers are excluded from the current proposal because many of the cognitive tests that are administered are language-based and are heavily influenced by first language). Subjects must also have no evidence of dementia (MMSE \geq 23) but some evidence of cognitive impairment (each subject will be required to answer in the affirmative: ‘do you have problems with memory and attention since having chemotherapy, and do you believe chemotherapy contributed to the problems?’). Each subject must be aware of the nature of his current medical condition and must be willing to give consent after being informed of the experimental nature of therapy, alternatives, potential benefits, side-effects, risks and discomforts. If a subject is determined to be cognitively impaired to the point of not meeting the above criteria at screening by the investigative team, they will not be included in this pilot phase of the clinical trial, making the use of proxy’s unnecessary.

4.3 Anticipated problems with subject recruitment and retention: Our group has extensive experience conducting research with breast cancer patients as well as studies collecting neuropsychological data, questionnaires, blood samples, and MRI/fMRI. Thus, we expect difficulties to be minimal. As with all clinical trials, we anticipate that there will a 10% loss of subjects to follow up, although, in our experience, breast cancer survivors tend to be a highly motivated group and the time between assessments is short and subjects will be required to come in monthly for monitoring safety and compliance. Moffitt Cancer center, as the only NCI designated Comprehensive cancer center in the State of Florida has a substantial number of subjects treated for breast cancer.

The recruitment, intervention and retention team (PI, [name], Co-I [name] and CRC) will initiate, develop and implement procedures to deal with and solve problems with attrition. As we have with our previous and current intervention trials, we will take measures to ensure that loss to follow-up is minimal, implementing several strategies for recruitment and retention as follows:

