12.2 Sample Size/Accrual Rate

In this pilot trial, we plan to accrue 40 evaluable subjects. This is a feasibility clinical trial in preparation to inform the design of a well-powered randomized clinical trial.

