12.7 Evaluation of Response

All participants included in the study will be assessed for response to intervention, even if there are major protocol deviations. We estimate that a minimum evidence of improvement in cognitive function with the 3 month intervention as indicated by a score of 1 standard deviation or more above population norms on the Hopkins Verbal Learning Test – Revised, Controlled Oral Word Association Test, or Color Trails Test Part 1 or 2 will be considered adequate to justify progression to a larger study.

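### Feasibility is a declared purpose, but accrual, retention and assessment completion are not analysed, and neither they nor adherence enter the rule for progressing to a larger trial

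*Combined protocol and SAP*

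**What the plan says.** **Purpose.** Section 3.0 describes a "randomized clinical trial of the feasibility of administering the nutritional supplement and placebo", and of performing cognitive testing, MRI and antioxidant assays before and after supplementation. Its list of what a feasibility study can show includes "Likelihood of patients agreeing to participate in the clinical trial" and projected enrolment, as well as effect-size and biomarker estimation. It closes: "The current feasibility pilot trial is to inform the research team of all these above challenges that occur with clinical trials". Each of the three aims in 2.1 repeats: "The current pilot study will evaluate the feasibility of administration of the nutritional supplement and placebo in this patient population". Section 12.2 adds: "This is a feasibility clinical trial in preparation to inform the design of a well-powered randomized clinical trial".

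**Endpoints and analysis.** The primary endpoints (8.1, 12.4, 12.6) are the number of impaired neuropsychological tests, framed as effect-size generation, and adverse events. Secondary and other endpoints (schema, 8.2, 12.5) are self-reported cognition, MRI, biomarkers and mediation, fatigue and depression. Sections 12.5.3 and 12.6 also plan to evaluate compliance from pill counts, diet records and blood levels, and to summarise discrepancies.

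**Progression.** Sections 8.1 and 12.7 say that a score at least 1 SD above population norms on the HVLT-R, COWA or Color Trails Part 1 or 2 "will be considered adequate to justify progression to a larger study". The only study-level stopping rule (11.4) concerns grade III or greater adverse events.

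**Working figures elsewhere.** Section 4.0: "we conservatively estimate that we will recruit and retain 40 subjects during the 6 months recruitment period". Section 4.3: "we anticipate that there will a 10% loss of subjects to follow up". Section 6.6 expects each participant to take at least 85% of study agent. Section 5.8 randomises a minimum of 40; section 12.2 plans 40 evaluable.

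**The concern.** A pilot that declares feasibility as a purpose should say which quantities answer that question, how they will be estimated, and how they bear on the decision to go on. Here the decision rule is written down, but it leaves those quantities out. The rule calls the cognitive score adequate, which makes it sufficient by itself. Slow accrual, heavy dropout, low capsule intake or many missing second scans would not alter the conclusion it gives.

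Recruitability was a live uncertainty. The May 2014 amendment letter reports that more than 90 potentially eligible patients were screened in 30 days and none qualified. That was under criteria since changed, so it says nothing about the current yield. It does show why the sponsor would want accrual reported and used.

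Timing matters too. Limits on retention or adherence chosen after the outcome data have been seen cannot serve as a decision rule.

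**Working it through.** **1. The plan's own figures.** The plan gives no target for a feasibility estimate. The sample size is argued only from efficacy effects. Reading the .23 in 12.4 as Cohen's f for the group-by-time interaction (my assumption), with N = 40, two time points and correlation .5: noncentrality = 0.23² × 40 × 2 / (1 − 0.5) = 8.46 on 1 and 38 df. Power is 0.81, against the stated .80. So that figure reproduces, but it concerns efficacy.

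**2. Each feasibility quantity against the plan.**

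| Quantity | Figure in the plan | Analysed in Section 12? | In the rule (8.1, 12.7)? |
|---|---|---|---|
| Accrual | 40 in 6 months (4.0) | No | No |
| Retention | 10% loss (4.3) | No | No |
| Agent intake | at least 85% per participant (6.6) | Descriptively (12.5.3, 12.6) | No |
| Both cognitive assessments done | none | No | No |
| Paired MRI, paired biomarkers | none | No | No |
| Effect size | .40 and .23 (12.4) | Yes | No; the rule uses scores against norms |

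**3. What 40 participants can show.** Exact (Clopper-Pearson) 95% limits for x of n are the 2.5% point of Beta(x, n − x + 1) and the 97.5% point of Beta(x + 1, n − x).

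- 36/40 = 90%: 76.3% to 97.2%. This is the result if loss is 10%.
- 24/40 = 60%: 43.3% to 75.1%. This is a hypothetical poor result. The interval excludes 90%, yet the rule would not register it.

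For accrual, 40 events have exact Poisson limits of χ²(0.025; 80 df)/2 = 28.58 and χ²(0.975; 82 df)/2 = 54.47. Divided by 6 months, the rate is 6.7 per month (4.8 to 9.1).

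**4. Whether a limit could discriminate.** Take, purely as an illustration, a requirement that at least 34 of 40 complete both cognitive assessments. By the binomial distribution it is met with probability 0.90 if true completion is 90%, 0.10 if it is 75% and 0.02 if it is 70%. The threshold of 34 is my assumption; the documents give none.

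**5. The denominator.** With 10% loss, 40 randomised leaves 40 × 0.9 = 36 evaluable. Ending with 40 evaluable needs 40 / 0.9 = 44.4, so 45 randomised. Sections 5.8 and 12.2 therefore imply different numbers unless more than the minimum are randomised.

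**The case against.** The strongest reply is that feasibility is not ignored. Compliance is evaluated in two subsections of Section 12. Section 3.0 counts effect-size and biomarker estimation as feasibility information, and generating effect sizes is the primary efficacy endpoint. Several other items on that list, such as competing trials, personnel and review timelines, are qualitative and would never be statistical endpoints. Retention and adherence are also managed in the conduct of the trial: retention procedures with weekly review of attrition (4.3), monthly pill counts and re-instruction (6.6, 7.7.7), and non-compliance as a reason for coming off agent or off study (8.3, 8.4). Finally, feasibility is not the only purpose. Each aim opens with an efficacy or mediation question, and 12.1 states an efficacy hypothesis.

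Most of this stands, and it limits the point. A reader might infer that the analysis plan contains no feasibility measure at all; 12.5.3, 12.6 and the effect-size endpoint contradict that. A reader might also infer that the rule could turn down a feasible larger trial. The text does not say so: it states what is enough to progress, not what would block progression. Nor does the 85% in 6.6 mean that 85% of participants must comply. It is an intake level expected of each participant.

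What remains is unanswered. Managing attrition during the trial is not the same as estimating it. The compliance summary has no defined proportion, no limit and no link to progression. Accrual, retention and completion of paired assessments have no planned analysis.

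**Conclusion.** The point holds within these limits. Beyond descriptive compliance and effect-size estimation, no feasibility outcome is defined or analysed, and none of accrual, retention, adherence or completion of paired cognitive, MRI and biomarker assessments enters the progression rule. As written, a cognitive score alone can justify a larger trial after, for instance, 24 of 40 retained.

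This should be fixed, and it is a cheap improvement. No planned analysis becomes invalid and no stated number is wrong because of it. It would go too far to say that feasibility must be a primary endpoint; the documents do not require that.

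The conclusion rests on reading the text of 2.1, 3.0, 8.1, 8.2 and Section 12, not on any calculation. The intervals assume 40 randomised as denominator and, for accrual, a constant rate. They are wide enough (76% to 97% at the anticipated retention) that the trial can recognise a clear failure but cannot separate neighbouring retention rates. The figures of 40 in 6 months and 10% loss are planning estimates, and the sponsor must decide whether to adopt them as references.

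**What to change.** **Add to Section 12**, as primary or secondary outcomes:

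1. Number randomised per month, with a Poisson 95% CI, against the planning figure of 40 in 6 months.
2. Proportion of randomised participants completing both cognitive assessments, against the anticipated 10% loss.
3. Proportion of participants whose pill count reaches at least 85% of study agent. The sponsor must set the pass mark for this proportion, since the protocol gives none.
4. Proportions with paired MRI and with paired biomarker samples.

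Report each proportion with an exact 95% CI.

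**Amend 12.7, and the matching text in 8.1**, so that the cognitive criterion is not sufficient alone and progression also requires retention and adherence limits. Fix those limits before outcome data are analysed.

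**Reconcile** the minimum of 40 randomised (5.8) with 40 evaluable (12.2) under 10% loss, and state the denominator for each outcome.

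**Screening and consent yield** should be reported only if a screening log is kept. The protocol names an eligibility checklist and a registration system but no log. Consent is signed at the screening visit, where eligibility checks are also made, so the denominators must be defined around that.

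**Cost.** Wording in 8.1, 12.2, 12.7 and a short addition to Section 12. Items 1 to 4 use randomisation records, pill counts and assessments already scheduled in Table 1 of 7.1, so no new procedure is needed. The downside is that the trial can miss a feasibility target it has stated.

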12.3 Randomization and Stratification

During the baseline/randomization visit, subjects will be randomized using block randomization. The current design will ensure equal number of subjects in each arm receiving radiation therapy post chemotherapy and concurrent endocrine therapy.

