4.1 Inclusion Criteria. 1) Women 30-70 years of age 2) Cases with Stage I-IIIB Breast Cancer that have completed neoadjuvant or adjuvant treatment with anthracyclines and/or taxanes + or –Radiation therapy within past 6 months (+/- 7 days) (subjects on concurrent endocrine therapy (TAM, Aromatase inhibitors are also eligible to participate as this is standard of care for this patient population) 3) Able to understand and sign the informed consent. 4) Fluent in reading, comprehension and communication in the English language. (Persons who are unable to meet this requirement are excluded from the current proposal because many of the cognitive tests that are administered are in English and translation of these instruments in other languages is currently unavailable) 5) No evidence of dementia (MMSE \geq 23) but some evidence of cognitive impairment (each subject will be required to answer in the affirmative: ‘do you have problems with memory and attention since having chemotherapy, and do you believe chemotherapy contributed to the problems?’); 6) Each subject must be aware of the nature of his current medical condition and must be willing to give consent after being informed of the experimental nature of therapy, alternatives, potential benefits, side-effects, risks and discomforts. 7) ECOG performance status of 0- 2 (8) Acceptable hemoglobin and hematocrit level based on CBC. (9) All subjects must be willing to be monitored for adequacy of nutritional intake during the intervention, as is the current standard of clinical practice.

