The research staff will use the Demographic Questionnaire Form to obtain baseline demographic data, medical and family history, and information regarding other health habits such as alcohol, tobacco and previous nutritional supplement use. Clinical Research Form (CRF): All medical record data (CRF) pertaining to the cancer diagnosis, tumor characteristics, node involvement, stage confirmation, medical history of cancer, menstrual cycle information, other medical history including renal or liver disease, concomitant medications including treatments for cancer and autoimmune diseases will be obtained from all subjects at baseline and changes in these variables monitored. Once clinical eligibility is confirmed, and informed consent is signed, randomization of subjects takes place within the Moffitt SRARS program. SRARS is a web delivered application that records subject registrations and provides randomization assignments. Subjects will be randomized to one of 2 groups. An email is sent to a list of pre-determined recipients (clinical research coordinators) stating the treatment/randomization assigned to the subject.

5.9 Blinding and Unblinding Methods: All requests to unblind treatment assignment will be directed to the Protocol Lead Investigators ([name], Moffitt Cancer Center & Research Institute, [contact], [contact], e-mail: [contact] . [name] will determine if disclosure of treatment assignment is required after consultation with the Medical Doctor who is the primary MD for the subject. If disclosure of the treatment would affect important medical decisions in a subject experiencing an AE, or could affect decisions regarding safe conduct of the clinical trial, unblinding might be allowed. If disclosure is warranted, the site will be directed to the product label found in the subject's CRF binder or other designated research record. The label has a scratch-off area that will disclose the treatment assignment. Each site will document the unblinding process in the patient chart.

6. AGENT ADMINISTRATION:

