12.4 Primary Endpoint

The primary efficacy endpoint is to generate effect sizes for changes in the number of impaired neuropsychological tests. The planned intervention period is three months. Neuropsychological outcomes will be examined using a 2 (group; COGNUTRIN, placebo) X 2 (time; baseline, three-months) repeated measures ANOVA to examine differences in the number of impaired neuropsychological tests. Age, premorbid cognitive functioning, depression and fatigue will be evaluated for association with neurocognitive performance and entered as covariates in statistical analyses if a marginally significant association ($p < .10$) is observed.

The primary efficacy endpoint is to generate effect sizes for changes in the number of impaired neuropsychological tests. The planned intervention period is three months. Neuropsychological outcomes will be examined using a 2 (group; COGNUTRIN, placebo) X 2 (time; baseline, three-months) repeated measures ANOVA to examine differences in the number of impaired neuropsychological tests. Age, premorbid cognitive functioning, depression and fatigue will be evaluated for association with neurocognitive performance and entered as covariates in statistical analyses if a marginally significant association ($p < .10$) is observed. The sample size of 20 patients per arm will allow us to generate useful information for future studies, in terms of anticipated effect size. Although this pilot study is not designed to be fully powered, the current sample size will allow us to detect an effect size difference of .40 for a one-tailed paired sample t-test, on account of the matched groups, at power of .80 and an alpha of .05. Moreover, the sample sizes will enable us to detect a group X time interaction of .23, with an alpha of .05, power of .80, and a stability coefficient of .5.

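### Section 12.3 promises equal arms on radiation and endocrine therapy, but the block randomisation it names cannot guarantee this, and no analysis names either factor

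*Combined protocol and SAP*

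**What the plan says.** Section 12.3 gives the method in one sentence: "During the baseline/randomization visit, subjects will be randomized using block randomization". The next sentence states the result expected of it: "The current design will ensure equal number of subjects in each arm receiving radiation therapy post chemotherapy and concurrent endocrine therapy". The section title contains the word Stratification. The text gives no stratification factors, strata, block size, or minimisation or matching procedure.

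Section 5.8 describes the allocation system and adds no strata: "SRARS is a web delivered application that records subject registrations and provides randomization assignments. Subjects will be randomized to one of 2 groups". Section 7.3 adds none either.

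Both factors vary among eligible women. Section 4.1 admits those who "completed neoadjuvant or adjuvant treatment with anthracyclines and/or taxanes + or –Radiation therapy within past 6 months", and allows concurrent endocrine therapy without requiring it. Section 12.2 sets the size: "In this pilot trial, we plan to accrue 40 evaluable subjects". Section 12.4 works with 20 per arm.

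The primary model in 12.4 is a group by time repeated measures ANOVA of the number of impaired tests. On covariates it says "Age, premorbid cognitive functioning, depression and fatigue will be evaluated for association with neurocognitive performance", and each enters only if its p-value is below .10. Elsewhere the protocol adds the WTAR score (7.7.9), cytokines (7.7.13), and medications, with psychotropic drugs as the examples (12.5.4). Radiation and endocrine therapy are named in no analysis.

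**The concern.** Blocking keeps the two arms close in size as accrual proceeds. It does nothing to equalise a patient characteristic unless the blocks are formed within levels of that characteristic. The only stated mechanism therefore does not deliver the stated property.

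The main product of this pilot is an effect size for a larger trial: "The sample size of 20 patients per arm will allow us to generate useful information for future studies, in terms of anticipated effect size". With 20 per arm, a difference of 4 subjects on a factor is 4/20 = 20 percentage points. The protocol itself gives some reason to care about endocrine status, since section 1.2 lists a sudden loss of steroid hormones among the proposed mechanisms of the impairment.

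The analysis has a matching gap. If two factors matter enough to be balanced by design, the model should carry them. Here neither is named, so the intended balance is not used in estimating precision, and any residual imbalance is not adjusted for.

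**Working it through.** **The plan's own figure.** The balance statement carries no number beyond equality. The only power figure for the primary model is the interaction in 12.4: effect size f = .23, alpha .05, power .80, stability .5, with 40 subjects and 2 time points.

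- Noncentrality: N × m × f² / (1 − ρ) = 40 × 2 × 0.0529 / 0.5 = 8.464.
- Noncentral F on 1 and 38 df: power 0.809. The stated .80 reproduces and is not in dispute.

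**Inputs for balance.** The total of 40 and the 1:1 split come from 12.2 and 12.4. The documents give neither the block size nor the prevalence of either factor. I assume blocks of 4 (and 2 as a variant), and prevalences from 30% to 80%.

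**Step 1: one factor, unstratified, number exposed fixed.** If K of 40 have the factor, the number X in one arm is hypergeometric (40, K, 20), and the between-arm difference is D = |2X − K|. For K = 20, P(D = 0) = C(20,10)² / C(40,20) = 0.248.

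| K | P(D = 0) | P(D ≥ 4) |
|---|---|---|
| 12 or 28 | 0.269 | 0.301 |
| 20 | 0.248 | 0.343 |
| 21 | 0 | 0.205 |
| 32 | 0.305 | 0.235 |

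The K = 21 row shows a parity effect. With an odd total, D can only be odd, so equality is impossible and P(D ≥ 4) drops. Results from a single even K should not be read as typical.

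**Step 2: both factors, number exposed random.** This was simulated with 8,000 trials of 40 subjects per setting and the two factors independent.

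| Radiation / endocrine prevalence (assumed) | Scheme | Equal on radiation | Equal on both | Difference ≥ 4 on either |
|---|---|---|---|---|
| 30% / 30% | unstratified, blocks of 4 | 12.8% | 2.0% | 41.1% |
| | stratified, blocks of 4 | 30.2% | 10.6% | 0.8% |
| 50% / 50% | unstratified, blocks of 4 | 12.0% | 1.6% | 46.6% |
| | stratified, blocks of 4 | 30.6% | 9.8% | 0.7% |
| 60% / 70% | unstratified, blocks of 4 | 12.5% | 1.4% | 41.6% |
| | stratified, blocks of 4 | 29.8% | 9.7% | 0.6% |
| 70% / 70% | unstratified, blocks of 4 | 13.4% | 1.6% | 40.1% |
| | stratified, blocks of 4 | 30.9% | 10.1% | 0.5% |
| 80% / 80% | unstratified, blocks of 4 | 15.2% | 2.5% | 29.7% |
| | stratified, blocks of 4 | 29.6% | 9.9% | 0.6% |

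Stratified blocks of 2 gave no difference of 4 or more, and equality on both factors in 15% to 17% of trials.

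**Step 3: why stratified blocks still miss equality.** Each stratum can end on an incomplete block. An incomplete block of 4 leaves an excess of at most 2 in one arm. Each factor level spans two strata, so the difference is at most 2 × 2 = 4. With blocks of 2 it is at most 2 × 1 = 2. The same incomplete blocks can unbalance the arm totals. The largest simulated difference was 6 with blocks of 4 and 4 with blocks of 2.

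**Step 4: effect on the estimate.** Suppose a factor shifts 3-month change by γ. A between-arm difference D then moves the estimated difference in change by γ × D / 20. For D = 4 and γ = 0.5 this is 0.10; for γ = 0.3 it is 0.06. If γ = 0 there is no shift. The documents give no value for γ.

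**Step 5: cost of adjusting.** Two more terms take the error df from 38 to 36. With the same noncentrality of 8.464, power is 0.808, against 0.809. This counts no gain from explained variance.

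**The case against.** The natural reading of 12.3 is stratified blocking, loosely worded. The title says Stratification, the text names exactly two factors, and the August 2013 amendment entry presents block randomisation as the means of balancing them. On that reading large imbalance is rare. This stands as evidence of intent, and the documents do not show how the allocation system was configured. A reader might infer that the trial was randomised without strata, but the text supports only that no strata are stated. The objection does not rescue the promise of equality, which stratified blocks also miss.

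A reader might also put the chance of a difference of 4 or more on at least one factor at 1 − (1 − 0.343)² = 57%. That fixes exactly 20 of 40 exposed on both factors, which nothing in the documents supports. Letting the number exposed vary gives about 30% to 47%.

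A third inference would be that imbalance biases the primary result. Chance imbalance under randomisation adds variance, not systematic bias. With two time points, the group by time test is a comparison of change scores, so a stable effect of either factor on the level of impairment drops out. Only an effect on 3-month change matters, and the documents do not establish one. The same condition limits any gain in precision from adjustment. The plan also says openly that it is an underpowered pilot. All of this stands and limits the point to specification and precision.

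Endocrine therapy could be read into the medication clause of 12.5.4, but it is not named there and would enter only if p < .10.

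**Conclusion.** The concern holds as a matter of specification. The assurance of equal numbers is wrong whether the blocks are unstratified (equality on one factor in about 12% to 15% of trials) or stratified with blocks of 4 (about 30%, and about 10% on both). What differs between the readings is the risk of a sizeable imbalance: about 30% to 47% for a difference of 4 or more on either factor without strata, and under 1% with them. That gap is why the strata need to be written down. These figures rest on assumed prevalences of 30% to 80%, independent factors, and blocks of 4.

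Neither factor is in any planned analysis. How much that matters depends on whether radiation or endocrine therapy influences 3-month change, which the documents leave open. The case for including both is that the trial means to balance on them and that including them costs almost nothing.

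**What to change.** In 12.3, state permuted blocks within the four radiation by endocrine strata, or minimisation on the two factors. Replace the assurance of equal numbers with a statement that the design will approximately balance the arms on both factors. Keep the block size concealed from the coordinators: under 5.8 they screen patients and receive the assignment by email, so a small known block could be guessed.

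In 12.4, include radiation and endocrine therapy as prespecified factors whatever their p-value, in one of two forms:

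- as factor by time terms in the repeated measures model, because main effects alone would not adjust the group by time contrast; or
- as covariates in an ANCOVA of the 3-month count adjusted for the baseline count. Baseline cannot simply be added to the repeated measures model, where it is already one level of time.

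The cost is a setting in the randomisation system, a short edit to 12.3 and 12.4 (a change of model if ANCOVA is chosen), about 2 degrees of freedom (power 0.809 to 0.808 at f = .23), and possibly slightly unequal arm sizes.
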